8.3.1 SAFETY OUTCOMES

8.3.1.1 ADVERSE EVENTS AND DEVICE DEFICIENCIES

Adverse events and device deficiencies will be summarized at each study visit based on the safety population for Cohort 1 and Cohort 2. The number and percentage of eyes reported with the ISO specified 12-month cumulative and persistent adverse events will be calculated for Cohort 1 and Cohort 2 separately. Additionally the events will be summarized for the HMIOL cohort (12-months after primary cataract surgery for Cohort 1 and 12-month after HMIOL optic exchange for Cohort 2). The corresponding one-sided lower 95% confidence limit will be calculated based on the binomial distribution and compared to the ISO SPE rate. If the one-sided lower 95% confidence limit is smaller than the SPE rate specified by ISO, then the null hypothesis of event rate of less than the SPE rate will not be rejected.

[REDACTED]

The ISO cumulative and persistent adverse events will also be provided for the fellow eye cohort and numerically compared to those of HMIOL eye cohort.

Additionally, the number and percentage of eyes reported with HMIOL-related adverse events during the study will be summarized for HMIOL Cohort 1, HMIOL Cohort 2, and HMIOL-eye Cohort. The two-sided 90% confidence interval of the percentage will also be provided.

8.3.1.2 [REDACTED]

[REDACTED]

[REDACTED]

[REDACTED]

[REDACTED]

[REDACTED]

[REDACTED]

[REDACTED]

[REDACTED]

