 15. Taking systemic medications that, in the opinion of the investigator, may confound the outcome or increase the risk to the subject (e.g. Tamsulosin Hydrochloride – Flomax) or other medications including anticholinergics, alpha adrenergic blocking agents with similar side effects (e.g. small pupil/floppy iris syndrome)
- 3.2.3 EXCLUSION CRITERIA DURING SURGERY
1. Vitreous loss prior to use of the investigational device
 2. Positive posterior pressure preventing safe implantation of the lens system
 3. Anterior chamber hyphema preventing visualization of implantation
 4. Any zonular or capsular rupture or capsular bag instability

CLARVISTA MEDICAL

PROTOCOL CP-00001 Rev.05

5. Intraoperative miosis preventing visualization of fixation features
6. Need for concomitant procedures (e.g. glaucoma surgery, LRI, RK, LASIK, etc.)
7. Subject who, in the clinical judgment of the investigator, is not suitable for participation in the study for another clinical reason, as documented by the investigator

3.2.4 EXCLUSION CRITERIA – 3 MONTHS POST-PRIMARY CATARACT EXTRACTION (AFFECTING ELIGIBILITY FOR HMIOL OPTIC EXCHANGE)

1. Any clinical finding or intraocular complication during primary cataract extraction that (in the judgment of the Investigator) is likely to increase complications with optic exchange procedure or present undue risk to the subject (e.g. unexplained endothelial cell loss, post-primary cataract extraction macular edema, persistent ocular inflammation, etc.)
2. Presence of YAG Capsulotomy in the primary (HMIOL) eye

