At the 3 month visit, an overall assessment of a subject's visual function will be performed by the physician. If the physician's assessment results in an opportunity for improved visual function through optic exchange in the test eye, the subject will be offered that opportunity. The Investigator and the Subject will decide if an optic exchange is appropriate.

The decision will be documented and the prospective Cohort indicated.

- If the subject has an acceptable outcome or it is otherwise decided an optic exchange will not take place, the subject will be entered into Cohort 1 and be followed at the 6 and 12 Month Visits prior to study completion. If the subject desires an exchange, however it is decided they cannot have one based on exclusion criteria (Section 3.2.4), the subject will remain in Cohort 1 and can utilize spectacles to correct RRE for the remainder of study participation. The investigator and subject can decide on further treatment per the Investigator's standard of care, following study participation.
- If it is decided an HMIOL optic exchange is desired, the appropriate pre-operative measurements will be obtained, 3 Month Visit assessments completed per Appendix A – Table 1, and HMIOL calculations and optic ordered. Finally, the subject will be scheduled for the procedure and entered into Cohort 2 (finalized after successful completion of optic exchange). If for any reason the optic exchange procedure does not take place, the subject will default back to Cohort 1.

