5.4. Safety Endpoints

All HMIOL Eyes Cohort

- [Redacted]
- [Redacted]
- Adverse event rates as compared to ISO 11979-7:2014 Annex B Safety and Performance Endpoint (SPE) tables including SSIs
- [Redacted]

Cohort 1 (No-Optic Exchange)

- [Redacted]
- AE rates as compared to ISO 11979-7:2014 Annex B Safety and Performance Endpoint (SPE) tables including SSIs
- [Redacted]

Cohort 2 (Optic Exchange)

- [Redacted]

Protocol CP-00001

ClarVista Medical, Inc.

A hypothesis test for this endpoint will be performed to assess whether mean percent change in ECC is no worse than 14%. The null and alternative are stated as:

$$H_0: \mu \geq 14\%$$

$$H_A: \mu < 14\%$$

Where μ represents the mean percent ECC loss from pre-exchange (3 months after the primary cataract surgery) to 3-month post-exchange for the eyes with HMIOL optic exchange (6 months after the primary cataract surgery). This test will be based on a one-sided, one-sample 0.05 t-test of a mean.

- [REDACTED]
- [REDACTED]
- AE rates as compared to ISO 11979-7:2014 Annex B SPE tables (includes SSIs –optic exchange procedures due to targeted residual refractive error are excluded)
- [REDACTED]

Fellow Eye Cohort

- [REDACTED]
- AE rates as compared to ISO 11979-7:2014 Annex B SPE tables including SSIs
- Dilated fundus examination

Adverse event rates in this study will be assessed as outlined in ISO 11979-7:2014 Annex B for posterior chamber IOLs. Following this methodology, for each specified adverse event we will calculate an exact lower one-sided 95% confidence bound for the proportion of eyes with the event at the one-year time point. As described in ISO 11979-7:2014 Annex B.3-B.4, success is defined as a lower bound that is less than the safety and performance endpoint (SPE) rate for that adverse event, in other words failing to reject the hypothesis that the event rate is greater than the SPE rate. The SPE rates for posterior chamber IOLs are provided in Table 1 below.

Table 1: Rates of Specific Adverse Events as Outlined in ISO 11979-7:2014 Annex B:

Adverse Event	Incidence Threshold
Cumulative	
Cystoid macular edema	3.0%
Hypopyon	0.3%
Endophthalmitis (inflammatory reaction (sterile or infectious) involving the vitreous body	0.1%
Lens dislocated from posterior chamber	0.1%
Pupillary block	0.1%
Retinal detachment	0.3%
Secondary surgical intervention (excluding posterior capsulotomies)	0.8%
Persistent	
Corneal stroma edema	0.3%

Protocol CP-00001

ClarVista Medical, Inc.

Cystoid macular edema	0.5%

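### Cohort-specific SPE verdicts are distorted because early complications help decide cohort membership; one verdict on all implanted eyes should govern

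*Protocol*

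**What the plan says.** Protocol 3.2.4 lets the investigator refuse an exchange for a finding or complication judged likely to raise its risk. The examples are "unexplained endothelial cell loss, post-primary cataract extraction macular edema, persistent ocular inflammation". A second bar is "Presence of YAG Capsulotomy in the primary (HMIOL) eye". Under Protocol 3.3.4, if a subject wants an exchange but "it is decided they cannot have one based on exclusion criteria (Section 3.2.4), the subject will remain in Cohort 1". The same section adds: "If for any reason the optic exchange procedure does not take place, the subject will default back to Cohort 1". Cohort 2 is therefore final only after a completed exchange.

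Protocol 8.3.1.1 states that ISO "12-month cumulative and persistent adverse events will be calculated for Cohort 1 and Cohort 2 separately". It also plans a summary of the two cohorts together, at 12 months from primary surgery for Cohort 1 and 12 months from exchange for Cohort 2. It then compares a one-sided lower 95% binomial limit with the SPE rate.

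SAP 5.4 lists the SPE comparison under All HMIOL Eyes, Cohort 1, Cohort 2 and Fellow Eyes, places it at one year, and gives the rule: "success is defined as a lower bound that is less than the safety and performance endpoint (SPE) rate for that adverse event". SAP Table 1 lists cystoid macular edema as a cumulative event (3.0%) and as a persistent one (0.5%). Iritis appears only as persistent (0.3%).

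SAP Section 4 restricts follow-up of the All HMIOL Eyes Cohort to the 3-month visit. SAP Section 2 says that the SAP supersedes the analyses in the protocol.

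**The concern.** Cohort membership depends partly on the outcome being counted. An eye with macular edema after primary surgery may be kept out of Cohort 2 because of that event. It then adds to Cohort 1's numerator, while event-free exchange candidates leave Cohort 1's denominator. Cohort 2 consists of eyes that passed a screen for the same kind of event. Neither cohort's cumulative rate estimates the event rate of the lens in implanted eyes, yet each receives a success or failure verdict.

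Two misreadings follow. A Cohort 1 failure could be put down to the lens when the rate in all implanted eyes meets the ISO limit. A clean Cohort 2 could be taken as evidence about the exchange procedure, or about the lens, when part of the cleanness comes from selection. The second matters more, because feasibility of exchange is a stated aim and the study is meant to inform a confirmatory trial.

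**Working it through.** **Inputs from the documents.** Minimum of 105 enrolled and 44 exchanges (Protocol 4.7.1), treated here as 105 implanted eyes, so Cohort 1 has 105 − 44 = 61. Enrollment of up to 200. SPE rate for cumulative cystoid macular edema 3.0% (SAP Table 1). Exact one-sided lower 95% limit (SAP 5.4).

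**Check of the binomial method on the plan's own figure.** The documents give no operating characteristic for the SPE rule. The nearest stated figure is the power in Protocol 8.1. With p0 = 0.925, true p = 0.85 and n = 100, the exact test rejects at 87 or fewer successes (actual alpha 0.0364). Power is 0.753, as printed.

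**Failure counts.** A cohort of n eyes fails at the smallest r with P(X ≥ r | n, 0.03) ≤ 0.05. This is equivalent to the exact lower limit exceeding 3.0%.

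- Cohort 1 (n = 61): r = 5. Lower limit for 5/61 is 3.29%; for 4/61 it is 2.27%.
- Cohort 2 (n = 44): r = 4.
- Pooled (n = 105): r = 7. Lower limit for 5/105 is 1.89%; for 6/105 it is 2.52%.

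**Effect of diversion.** Assumptions: the true rate p is the same in all implanted eyes; all events precede the 3-month decision; cohort sizes are fixed; pre-exchange events count in Cohort 2; exchange adds none. A share f of the events that would have fallen in Cohort 2 moves to Cohort 1. The documents do not give f, so a range is shown.

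- Cohort 1 rate: q1 = p × (1 + f × 44/61)
- Cohort 2 rate: q2 = p × (1 − f)

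At p = 0.03 and f = 0.5, q1 = 0.03 × (1 + 0.5 × 0.721) = 0.0408 and q2 = 0.015. At f = 1, q1 = 0.0516 and q2 = 0.

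Chance of failing at p = 3.0%:

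| f | Cohort 1 (fails at 5) | Cohort 2 (fails at 4) | Pooled (fails at 7) |
|---|---|---|---|
| 0 | 0.036 | 0.042 | 0.039 |
| 50% | 0.103 | 0.004 | 0.039 |
| 75% | 0.151 | <0.001 | 0.039 |
| 100% | 0.206 | 0 | 0.039 |

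**Other true rates at 61/44.** At 2.0%, Cohort 1's chance goes from 0.008 (f = 0) to 0.059 (f = 100%). At 9%, three times the SPE rate, Cohort 2's chance of failing falls from 0.57 to 0.14 (50%) and 0.02 (75%), while the pooled chance is 0.84.

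**Larger study, p = 3.0%, f from 0 to 100%.** With 156/44, Cohort 1 goes from 0.047 to 0.149. With 116/84, it goes from 0.024 to 0.252.

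**Persistent events at 61/44.** Persistent macular edema fails at 2 events in Cohort 1 and 3 pooled. Persistent iritis and corneal stroma edema fail at 2 in either, so for those the Cohort 1 and pooled verdicts differ little.

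**The case against.** The strongest reply is that an unselected analysis already exists. Protocol 8.3.1.1 pools both cohorts at 12 months, and SAP 5.4 lists the SPE comparison under All HMIOL Eyes. A reader might infer from the cohort-specific rates that no such analysis is planned; that would be wrong. What remains is that the pooled result has no stated precedence over the cohort verdicts and mixes time origins. The superseding SAP also stops that cohort's follow-up at 3 months while setting the SPE test at one year.

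A reader might also infer that channelling alone will make Cohort 1 fail. Five macular edema cases at 61/44 do reverse the verdict (3.29% against 1.89% pooled), but only if all five are in Cohort 1. With one in Cohort 2, 4/61 passes. At 156/44, 5/156 has a lower limit of 1.27% and passes. The bar is at the investigator's discretion, so full diversion is an upper end. Nor is Cohort 2 certain to look clean: a second operation can add events, and at n = 44 a single endophthalmitis exceeds its 0.1% limit.

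Further points stand in part. Early inflammation that bars exchange need not become a counted persistent iritis. No test between cohorts is planned. Eyes eligible under 3.2.4 are a meaningful population for studying exchange. SAP Section 4 already splits Cohort 2 follow-up at the exchange, although no visible text says which period feeds the SPE count. Text after the SPE rule in Protocol 8.3.1.1 is blacked out, so a qualifier there cannot be excluded.

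**Conclusion.** The point holds as a bias in the cohort-specific SPE verdicts: Cohort 1 toward failure, Cohort 2 toward success. It does not hold as a prediction that either verdict will be wrong, nor as a claim that every comparison is affected.

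For cumulative cystoid macular edema at the 105/44 minimum and a true 3.0%, Cohort 1's chance of failing rises about threefold at 50% diversion (0.036 to 0.103) and nearly sixfold at the upper end (0.206). Cohort 2's all but vanishes. For events counted only as persistent the effect is smaller. The size rests on the assumed diverted share and on events preceding the 3-month decision. The Cohort 2 figures also assume that pre-exchange events count there, which the visible text leaves open.

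The consequence is moderate, since SAP Section 4 says the tests are not meant for definitive regulatory conclusions. The correction is inexpensive and worth making.

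**What to change.** In Protocol 8.3.1.1 and SAP 5.4:

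1. Name the comparison in all implanted eyes, counted from primary surgery over a stated one-year window, as the SPE verdict. Reconcile the 3-month limit in SAP Section 4 with the one-year rule in SAP 5.4 so that it can be computed.
2. State which visit supplies persistent-event status for exchanged eyes. Their visits run from the exchange: at day 81 to 121 after primary surgery (day 80–100 plus 1–21), the 12-month window of day 330–420 becomes day 411 to 541. Cumulative events can be counted by onset date. Carry the exclusion of planned exchanges from secondary surgical interventions into the pooled count.
3. Report Cohort 1 rates and Cohort 2 pre-exchange rates descriptively, without an SPE verdict.
4. Limit any Cohort 2 SPE comparison to events with onset on or after the exchange date, and note that these eyes were screened under 3.2.4.
5. Tabulate the eyes barred under 3.2.4, by reason, so that the diverted share is known.

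The clinical bar itself is untouched. The cost is wording in both documents on essentially the same data. The sponsor gives up a separate SPE verdict for Cohort 1, which has no clear interpretation under this selection.

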APPENDIX A – TABLE 2: SCHEDULE OF ASSESSMENTS – FELLOW EYE

Table 2	Fellow Eye Cohort						
	Op-Visit 2 Fellow Eye Implant (Day 0 +7-30 Days)	Form 1.1 FE 1 Day Visit (Day 1-2)	Form 2.1 FE 1 Wk Visit (Day 7-14)	Form 3.1 FE 1 Mo Visit (Day 30-60)	Form 4.1 FE 3 Mo Visit (Day 80-100)	Form 5.1 FE 6 Mo Visit (Day 120-180)	Form 6.1 FE 12 Mo Visit (Day 330- 420)
Eligibility	X						
UCDVA		X	X	X	X	X	X
Manifest Refraction				X	X		X
BCDVA				X	X		X
[REDACTED]		■	■	■	■	■	■
[REDACTED]					X	X	X
Capsule Assessment						■	■
Dilated Fundus Exam					X		X
Fellow Eye Surgery	X						

APPENDIX A – TABLE 3: SCHEDULE OF ASSESSMENTS – COHORT 2

Table 3	Cohort 2 - Optic Exchange Complete						
	Op-Visit 3 Optic Exchange Visit (3 Mo Visit +1-21 Days)	Form 1.2 OE 1 Day Visit (Day 1-2)	Form 2.2 OE 1 Wk Visit (Day 7-14)	Form 3.2 OE 1 Mo Visit (Day 30-60)	Form 4.2 OE 3 Mo Visit (Day 80-100)	Form 5.2 OE 6 Mo Visit (Day 120-180)	Form 6.2 OE 12 Mo Visit (Day 330- 420)
Eligibility	X						
UCDVA ²³		X	X	X	X	X	X
Manifest Refraction			X	X	X	X	X
BCDVA			X	X	X	X	X
Keratometry ²⁴				X	X		X
Axial Length				X	X		X
[REDACTED]		■	■	■	■	■	■
Slit Lamp Examination		X	X	X	X	X	X
[REDACTED]					■	■	■
[REDACTED]					■	■	■
IOP		X	X	X	X	X	X
Lens / Capsule Assessment ²⁵					X	X	X
[REDACTED]		■	■	■	■		■
[REDACTED]		■	■	■	■		■
[REDACTED]		■	■	■	■		■
Dilated Fundus Exam					X		X
Optic Exchange Procedure	X						

²³ If UCDVA is <20/40, perform Pinhole (PH) vision

²⁴ Measurements via biometry

[REDACTED]

[REDACTED]	[REDACTED]	[REDACTED]
[REDACTED]	[REDACTED]	[REDACTED]
[REDACTED]	[REDACTED]	[REDACTED]
[REDACTED]	[REDACTED]	[REDACTED]
[REDACTED]	[REDACTED]	[REDACTED]

Date/Time (mm/dd/yyyy GMT):	Signed by:	Justification:
[REDACTED]	[REDACTED]	[REDACTED]
[REDACTED]	[REDACTED]	[REDACTED]

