1 TITLE PAGE

Protocol Number:	ClarVista CP-00001
Medical Specialty:	Surgical
Project Name /Number:	NA
Sponsor Name & Address:	CLARVISTA MEDICAL, INCORPORATED [name] [name] [contact] [contact]
Test Article(s) / Product(s):	ClarVista HARMONI® Modular Toric Intraocular Lens System

Protocol CP-00001

ClarVista Medical, Inc.

Statistical Analysis Plan for Protocol CP-00001

Sponsor

ClarVista Medical, Incorporated
[name]
[name]
[contact]
[contact]

Original Version Date

24 February 2017

Protocol CP-00001

ClarVista Medical, Inc.

Table of Contents

1. Purpose	3
2. Scope.....	3
3. Software.....	3
4. Design and Objectives.....	3
5. Statistical Analyses.....	4
6. Sample Size	7
7. Analysis Populations	7
8. Sensitivity Analyses.....	8
9. Subgroup Analyses.....	8
	
11. Deviations from the Statistical Analysis Plan.....	9
12. References	9

Protocol CP-00001

ClarVista Medical, Inc.

1. Purpose

This Statistical Analysis Plan documents and describes the planned analyses for the CP-00001 CLEAR study. This is a feasibility study of the ClarVista HARMONI Modular Intraocular Lens System for the Treatment of Aphakia Following Cataract Surgery.

The intent of the study is to demonstrate the

- Feasibility of HARMONI IOL (HMIOL) implantation and assembly in subjects undergoing cataract surgery
- Feasibility of the HMIOL optic component exchange procedure (performed 3 months following primary cataract extraction)

Safety and effectiveness of these procedures will be characterized with the intent of supporting a future confirmatory study.

2. Scope

This document is based on the Investigational Plan CP-00001, Rev.05. Changes to the Investigational Plan may require updates to this document. Analyses described here expand on and supersede those described in the Investigational Plan.

3. Software

Statistical analyses will be performed with SAS System Software version 9.4 or above (SAS Institute, Cary, N.C.), R version 3.3 or above (R Core Team, <http://www.R-project.org>), or other validated statistical software package.

4. Design and Objectives

The CP-00001 study is designed as a prospective, multi-center, cohort study. Any pre-planned formal hypothesis tests for this feasibility study are not for the purposes of generating definitive conclusions to support regulatory approval.

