Several cohorts of subjects are specified to help characterize the clinical significance of the study outcomes in eyes with and without optic exchange. These cohorts are defined as follows:

All HMIOL Eyes Cohort: Defined as all study eyes implanted with the study device. Analysis of follow-up visits for this cohort definition is restricted to 1 Day, 1 Week, 1 Month, and 3 Months following primary cataract extraction (PCE).

Cohort 1: Defined as the subset of study eyes implanted with the study device without a subsequent optic exchange procedure. Analysis of follow-up visits for this cohort definition is restricted to 1 Day, 1 Week and 1, 3, 6 and 12 Months following primary cataract extraction.

Cohort 2: Defined as the subset of study eyes implanted with the study device with a subsequent optic exchange procedure. Analysis of follow-up visits for this cohort will cover two time periods:

- Pre-Optic Exchange, comprising 1 Day, 1 Week, 1 Month, and 3 Months following primary cataract extraction, prior to the optic exchange visit.
- Post-Optic Exchange, comprising 1 Day, 1 Week, 1 Month, 3 Months, 6 Months, and 12 Months following optic exchange. The baseline for the post-optic exchange visits is the 3 Month pre-optic exchange visit.

Fellow Eyes Cohort: Defined as the contralateral eyes not implanted with the study device. Analysis of follow-up visits for this cohort definition is restricted to 1 Day, 1 Week, 1 Month, 3 Months, 6 Months, and 12 Months following primary cataract extraction.

Separate analyses are planned for each cohort.

Protocol CP-00001

ClarVista Medical, Inc.

5. Statistical Analyses

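### The all-eyes adverse-event rate compared with the one-year ISO limits has no single one-year clock: the protocol mixes two time origins, and the SAP stops the pooled cohort at 3 months

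*Protocol*

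**What the plan says.** Protocol 8.3.1.1 says that "ISO specified 12-month cumulative and persistent adverse events will be calculated for Cohort 1 and Cohort 2 separately". It then adds a summary for the combined HMIOL cohort, timed at "12-months after primary cataract surgery for Cohort 1 and 12-month after HMIOL optic exchange for Cohort 2". The decision rule is: "The corresponding one-sided lower 95% confidence limit will be calculated based on the binomial distribution and compared to the ISO SPE rate".

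SAP section 2 states: "Analyses described here expand on and supersede those described in the Investigational Plan". SAP section 4 ends follow-up of the All HMIOL Eyes Cohort at 3 months after primary extraction and plans a separate analysis for each cohort. It gives Cohort 2 a pre-exchange and a post-exchange period and adds: "The baseline for the post-optic exchange visits is the 3 Month pre-optic exchange visit". SAP section 5.4 nevertheless lists the SPE comparison for the All HMIOL Eyes Cohort as well as for Cohorts 1 and 2. It specifies an "exact lower one-sided 95% confidence bound for the proportion of eyes with the event at the one-year time point" and does not say from which operation the year runs. "The SPE rates for posterior chamber IOLs are provided in Table 1 below": seven cumulative rows and four persistent rows.

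Protocol 6.0 collects adverse events from consent to the last visit, which for Cohort 2 is 12 months after exchange.

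**The concern.** A cumulative incidence can be set against a one-year benchmark only if every eye is counted from the same kind of starting point over one year. The protocol's pooled rate gives exchanged eyes a different end point and leaves their starting point open. The SAP's pooled cohort ends at 3 months, so it cannot supply a one-year rate at all.

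At stake is the all-eyes safety verdict, the only SPE comparison that covers every implanted eye. The limits are low and the sample is small, so one event included or left out can change a row. Two analysts following the documents in good faith could report different results.

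**Working it through.** **Is there a figure to reproduce?** Neither document gives a numerical result or power for the SPE comparison. The power table in protocol 8.1 concerns BCDVA, not adverse events. It does reproduce with the exact binomial: at n = 100 the test rejects at 87 or fewer successes, and the power is 0.753. Exact binomial limits are also what SAP 5.4 specifies, so I use them below.

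**Follow-up from implantation** (protocol 3.3.4, 3.3.6 and Appendix A; Table 3 places the "Optic Exchange Visit (3 Mo Visit +1-21 Days"):

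- Exchange: Day 80 + 1 to Day 100 + 21 = Day 81-121.
- Cohort 1 final visit: Day 330-420.
- Cohort 2 final visit: 81 + 330 to 121 + 420 = Day 411-541, about 13.5 to 17.8 months.
- Difference: 411 - 330 = 81 days to 541 - 420 = 121 days.
- Cohort 2 six-month visit: 81 + 120 to 121 + 180 = Day 201-301. Exchanged eyes therefore have no scheduled visit of their own between Day 301 and Day 411.

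With 44 exchanged eyes among 105 (the minimums in protocol 4.7.1) and nominal times of 12 and 15 months, average follow-up is (61 × 12 + 44 × 15)/105 = 1392/105 = 13.3 months.

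**What the all-eyes cumulative rate could mean:**

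| Reading | Cohort 1 | Cohort 2 |
|---|---|---|
| SAP section 4 | 0-3 months | 0-3 months |
| Protocol 8.3.1.1, all events counted | 0-12 months | 0 to about 15 months, including the exchange |
| Protocol 8.3.1.1, count restarted at exchange | 0-12 months | about 3 to 15 months, including the exchange |

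No row is 0-12 months from implantation for every eye.

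**How close the verdicts are.** Exact one-sided lower 95% limit for k events in n eyes: the 5th percentile of Beta(k, n - k + 1). At n = 105:

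| SPE (cumulative rows) | Largest k that passes | Next k, which exceeds |
|---|---|---|
| 0.1% | 1 event: 0.05% | 2 events: 0.34% |
| 0.3% | 1 event: 0.05% | 2 events: 0.34% |
| 0.8% | 3 events: 0.78% | 4 events: 1.31% |
| 3.0% | 6 events: 2.52% | 7 events: 3.17% |

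**How far the counting rule can move the result.** Illustration for cumulative cystoid macular edema, with the true one-year rate r set at the 3.0% limit, 61 unexchanged and 44 exchanged eyes. Let e be the share of one-year risk that falls in the first 3 months. The documents do not give e, so I assume a range of 25% to 100%. Risk after 3 months is taken as constant, so 12 later months carry r(1 - e) × 12/9. The pooled rate is (61r + 44p)/105, where p is the Cohort 2 rate. On one clock p = r, and the chance of 7 or more events is 3.9%.

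| Rule for Cohort 2 | p | Pooled rate, e = 25% to 100% | Chance of 7 or more events |
|---|---|---|---|
| Restart, exchange adds no risk | r(1 - e) × 12/9 | 3.0% to 1.74% | 3.9% to 0.2% |
| From implantation, exchange adds no risk | re + r(1 - e) × 12/9 | 3.31% to 3.0% | 6.1% to 3.9% |
| From implantation, exchange repeats the full risk | 1 - (1 - re)(1 - r) | 3.31% to 4.22% | 6.0% to 15.5% |
| Restart, exchange repeats the full risk | r | 3.0% | 3.9% |

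Check of the first row at e = 100%: 61 × 3.0%/105 = 1.74%.

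**The case against.** The strongest reply is that the SAP governs, plans separate analyses by cohort and does not repeat the two-origin pooled rate. That is right about where the correction belongs. It does not remove the problem, because SAP 5.4 still lists the SPE comparison for all HMIOL eyes at one year while SAP section 4 ends that cohort at 3 months. Protocol 8.3.1.1 is the only text that defines a pooled one-year rate.

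A second reply is that Cohort 1 is reported separately and already runs 12 months from implantation. That stands, but Cohort 1 leaves out every exchanged eye, and Cohort 2's own one-year rate has the same unstated origin.

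A third is that the study is a feasibility study, no SPE test is powered, and the SAP disclaims definitive conclusions. That limits the consequence. A missing definition still needs supplying when the results are meant to inform a confirmatory study.

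A reader might infer that the plan discards Cohort 2 events before exchange. The documents do not support that. The SAP's 3-month baseline is stated for post-exchange visits, the same section keeps Cohort 2's pre-exchange period, and protocol 6.0 collects events from consent. Counting all events is the more natural reading; it lengthens exposure and errs against the device. A restart remains possible only because no rule excludes it.

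**Conclusion.** The point holds as a definitional gap in the cumulative SPE comparison for all HMIOL eyes. As written, the rate is a 3-month rate (SAP section 4) or joins about 12 months from implantation with a period ending about 15 months from implantation (protocol 8.3.1.1). Neither matches a one-year SPE.

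A reader might go further and conclude that the rate is biased in a known direction, or that a fixed share of events is lost. That does not follow. Counting from implantation gives exchanged eyes 81 to 121 more days and pushes the rate up. Restarting at exchange would drop early events, but the net shift is nil if the exchange repeats the surgical risk, or if risk is constant over time and the exchange adds none. In the illustration, the chance of exceeding the 3.0% limit runs from 0.2% to 15.5%, against 3.9% on one clock. That range rests on the assumed timing of risk and on 44 of 105 eyes (42%) being exchanged. Those are minimums for an optional early stop; 44 of 200 would be 22%, and the effect smaller.

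What does not rest on those assumptions is the missing rule, the visit arithmetic and, at 105 eyes, the one-event margins. The correction is worth making before analysis.

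**What to change.** 1. **Cumulative rows, all HMIOL eyes.** Count every implanted eye from Day 0 to 12 months after primary implantation, including events before and after exchange. State that planned optic exchanges are not themselves SSIs here, as both documents already say for Cohort 2. The exclusion is not written for the pooled cohort, and 44 exchanges counted among 105 eyes would give a lower limit of 33.8% against 0.8%.
2. **Exchange procedure.** Report Cohort 2 from exchange to 12 months post-exchange in a separate table with its exact limit.
3. **Persistent rows.** Keep the assessment at each cohort's final 12-month visit, report by cohort and label the time origin. A single implantation clock cannot serve these four rows, because exchanged eyes have no scheduled visit between Day 301 and Day 411.
4. **Reconcile** SAP sections 4 and 5.4 with protocol 8.3.1.1, so that the follow-up of the All HMIOL Eyes Cohort matches its one-year comparison.

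The cost is a short SAP amendment and one extra table. No new visits are needed: SAP 5.5 already relies on event onset dates. The pooled rate will still include the effect of a second operation within the year, which should be stated beside it. Cohort 2 events later than 12 months after implantation will appear only in the exchange table.
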